This study is a randomised, double-blinded, superiority clinical trial with six parallel groups. The hypothesis tested to evaluate two early childhood tooth caries treatment methods with two different application protocols, comparing a placebo, will be performed at the Rīga Stradiņa University's (RSU) Institute of Stomatology Children's Dentistry department.

Participants

According to the AAPD's (American Academy of Pediatric Dentistry) definition of severe early childhood caries (S-ECC) is a condition when a child up to 3 years old has at least one caries damage without cavitates and from 3 to 5 years old with at least one caries damage with cavitates (AAPD). Every week approximately 15 children ages 2-6 years-old with multiple caries damage seek consultations about the possibility to receive planned tooth treatment under general anaesthesia (GA) at the RSU Institute of Stomatology. After confirmation of the diagnosis, the children are put on a waiting list for treatment, which lasts 12 months. These children are offered to participate in this study, while they wait for rehabilitation with general anaesthesia. Every day approximately 10 children arrive that are at an age to be included in the study, with acute pain or an infection. They are also given the opportunity to participate in the study, if they conform with the criteria. As a result, the patient's involved in the study have common characteristics: multiple caries damage with cavities (indicating restorative treatment); a high level of caries risk factors; possible difficulties with behavioural control. To bring the study's sample patients as close as possible to the overall children's population, participants will be included according to defined criteria.

Inclusion criteria:

- children aged 2-6;
- have at least one active caries damage with cavitates (comply with the diagnosis of S-ECC);
- wish to participate in the study;
- parents agree to participation in the study and sign a consent form.

Exclusion criteria:

- the child arrives with an adult who doesn't have the right to sign a consent form, and the person responsible for the child cannot be present;
- chronic or serious acute general illness;
- in the last month has used medications, that could affect the secretion of saliva;
- previously received treatment with products that have a high level of fluoride concentration.

Sample size calculation

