The calculation of sample size was based on the question: "Which of the applied caries treatment methods will have the least frequency of complication occurrences, treating severe early childhood caries in children from the ages of 2 to 6 years-old?" Since we will compare proportions in six groups, in the sample size calculation we used formulas, which are shown in Fig 1 (Shao, Chow and Wang, 2003), calculating that the planned number of various proportions for comparison will be 9.

From previous studies it is known that conventionally treating early childhood tooth caries, the frequency of complications is 10% (Innes *et al.*, 2013), but, examining clinical cards at RSU's Institute of Stomatology Children's Dentistry department, the frequency of complications for children that are waiting in line for treatment with general anaesthesia and who receive no additional treatment, is approximately 30%, therefore in the study's treatment groups we expect that the frequency of complications will be no greater than 10%, but in the placebo groups - 30%. From the calculations in the formulas above, we calculated, that for the study we need 49 children in each group, to ascertain the difference in complication proportions between 30% un 10% with α error 0.05 and with a study capacity of 80%. Together 294 children are necessary but, calculating possible losses during the observation time, it is planned to involve 70 children in each group, therefore, 420 in six groups.

$$n = (p_A(1 - p_A) + p_B(1 - p_B)) \left(\frac{z_{1-\alpha/(2\tau)} + z_{1-\beta}}{p_A - p_B} \right)^2$$

$$1 - \beta = \Phi(z - z_{1-\alpha/(2\tau)}) + \Phi(-z - z_{1-\alpha/(2\tau)}) \quad , \quad z = \frac{p_A - p_B}{\sqrt{\frac{p_A(1-p_A)}{n} + \frac{p_B(1-p_B)}{n}}}$$

Fig 1. Formulas to calculate the sample size. n = the sample size (for one comparison, therefore two equivalent groups); Φ = standard normal allocation function; α = I type error; τ = number of comparisons; β = II type error; $1-\beta$ = study capacity.

Randomization, allocation and blinding

Flow chart of research methodology is shown in Fig 2. If the patient fulfills the inclusion criteria, their parents (caregiver) will be offered the opportunity to participate in the study. The objective of the study will be explained both verbally and in writing, as well as the expected results and side effects of the treatments:

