1. The first placebo group – placebo varnish application twice with a six-month interval and a recommendation to brush teeth with a toothpaste containing fluoride (F content of at least 1000 ppm);
2. The second placebo group – placebo varnish application four times with a week's interval and a recommendation to brush teeth with a toothpaste containing fluoride (F content of at least 1000 ppm);
3. The first SDF group – Riva Star SDF (35-40% silver fluoride, 15-20% ammonium) application twice with a six-month interval and a recommendation to brush teeth with a toothpaste containing fluoride (F content of at least 1000 ppm);
4. The second SDF group - Riva Star SDF application four times with a week's interval and a recommendation to brush teeth with a toothpaste containing fluoride (F content of at least 1000 ppm);
5. The first Tiefenfluoride group – Tiefenfluoride (0,4% $\text{CuSiF}_6 \times 6 \text{H}_2\text{O}$, 10,9% $\text{MgSiF}_6 \times 6 \text{H}_2\text{O}$, 0,1% NaF, 9,6% $\text{Ca}(\text{OH})_2$) application twice with a six month interval and a recommendation to brush teeth with a toothpaste containing fluoride (F content of at least 1000 ppm);
6. The second Tiefenfluorid group - Tiefenfluorid application four times with a week's interval and a recommendation to brush teeth with a toothpaste containing fluoride (F content of at least 1000 ppm);

The goal of the treatment is to stop the progress of the existing damage progress and avert the formation of new damage; caries tissue removal will not be performed; the products will be applied to dried teeth.

For ethical reasons, the negative control group will not be used – in each of the study’s groups the parents (direct caregivers) will be given advice about tooth cleaning and diet, using motivational intervention principles and recommending brushing teeth with toothpaste that contains fluoride (at least 1000 ppm), which is defined as non-restorative caries treatment and which has also proven its effectiveness in stopping caries damage.

Outcome variables

Patients will be examined at the baseline and at 12 months.

The patient’s primary examination will determine the following parameters:

- 1) general information about the child (birth date, gender, medical health history);
- 2) hygiene and dietary habits (frequency of brushing teeth; are teeth cleaned by the child or by parents; the fluoride concentration in toothpaste);
- 3) plaque (visible/invisible);

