- 4) the level and development of the caries damage and activity (ICDAS, Nyvad criteria).

Outcome measures:

- I. Primary outcome measures:
 - A. Pain history during the observation period, assessed as Yes/No at 12 months follow-up visit.
 - B. Abscess history during the observation period, assessed as Yes/No at 12 months follow-up visit.
 - C. The number of newly extracted or otherwise surgically treated teeth during the observation period, assessed as a number of extracted teeth during the last year at 12 months follow-up visit.
- II. Secondary outcome measures:
 - A. The change in the overall activity of caries as Active/Non-active, assessed at 12 months follow-up visit.
 - B. The progression and change of activity of every lesion, assessed by ICDAS (for progression) and Nyvad (for activity) criteria, at 12 months follow-up visit.
 - C. The parent’s satisfaction with the way their children’s teeth look, assessed by questionnaire, asking: “Are you satisfied with the way your child’s teeth look?”

- and “Would you agree to repeat the treatment procedure used?”, both measurements in 5-point Likert scale, assessed at 12 months follow-up visit.
- D. The child’s satisfaction with their teeth, measured by the visual analogue scale (VAS) with 3 points - happy, not sure, sad, assessed at 12 months follow-up visit.
 - E. The child’s feelings during the treatment, measured by the modified Wong-Baker scale with 3 options - no hurt, hurts a little, hurts a lot), assessed during every appointment (depending on treatment group can be assessed at baseline, 1, 2, 3 weeks and 12 months; or at baseline, 6 and 12 months).
 - F. The direct costs of the treatment and the cost-effectiveness, calculated as EUR spent per treatment protocol; EUR per prevented major complications (in patient-level - pain, abscess, extraction) and EUR per prevented minor complications (in tooth-level - progression of caries lesion), the calculation will be made at 12 months follow-up.
 - G. The treatment method’s undesirable side effects, assessed by parents’ questionnaire at the 12 months follow-up visit.

Statistical analysis

Data will be digitized, by entering in an ad-hoc form in the Google Docs programme. Further the data will be exported cvs (comma separated values) to an archive. Missing data will be eliminated from the analyses, marking them NA.

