Data will be exported in the statistics programme R (R Core Team, 2013), and program packages Tidyverse (Wickham, 2017) un Lubridate (Grolemund and Wickham, 2011) will be used for data processing.

Ethics

The study will be performed in accordance with the Helsinki Declaration (World Medical Association, 2013), and will observe personal data protection.

The patient will be offered to voluntarily choose, whether to participate in the study, ensuring, that if they decline, they will receive the same quality conventional treatment. The patients involved will be the ones that are waiting in line for state-funded restorative caries treatment under general anaesthesia, therefore, the possibility to participate in the study can be viewed as an additional treatment, which the children can receive during the waiting period. All the patients – both those that

participate in the study, as well as those who decline, if during the waiting period an emergency situation arises which requires immediate intervention, it will be ensured according to standard protocol at the Institute of Stomatology Children's Dentistry department.

In the attachment you can find the parent's informed consent form (1st attachment), a questionnaire for the children (2nd attachment), a description of acute aid form (3rd attachment) and a clinical examination form (4th and 5th attachment). Using ad hoc, the forms data will be digitized, entering the data anonymously and ensuring, that patients cannot be identified from the stored data.

Safety

The medications used are registered for use in professional caries treatment:

1. Riva Star SDF (35-40% silver fluoride, 15-20% ammonium) (SDI Limited, 2015);
2. Tiefenfluorid (0,4% $\text{CuSiF}_6 \times 6 \text{H}_2\text{O}$, 10,9% $\text{MgSiF}_6 \times 6 \text{H}_2\text{O}$, 0,1% NaF, 9,6% $\text{Ca}(\text{OH})_2$) (Knappwost-Gieseke, 2002).

Work packages

Work breakdown structure can be seen in Fig 3.

[figure not shown]

Fig 3. Work packages of the clinical trial.

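### Children presenting with acute pain or infection may be enrolled, but the listed baseline data and outcome definitions cannot separate an episode present at entry from a new primary event

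*Protocol*

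**What the plan says.** **Who is enrolled.** Protocol, Participants, describes two routes. The first is the GA waiting list: "Every week approximately 15 children ages 2-6 years-old with multiple caries damage seek consultations". The second is children who attend with acute pain or infection: "Every day approximately 10 children arrive that are at an age to be included in the study, with acute pain or an infection". Of these it says: "They are also given the opportunity to participate in the study, if they conform with the criteria". The only exclusion that refers to illness is "chronic or serious acute general illness", which does not cover dental pain, a dental abscess or a tooth that already needs extraction. Protocol, Ethics, gives a different population: "The patients involved will be the ones that are waiting in line for state-funded restorative caries treatment under general anaesthesia".

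**Planning rate.** Protocol, Sample size calculation, takes the 30% placebo complication rate from clinic records of "children that are waiting in line for treatment with general anaesthesia". The treatment groups are assumed to have at most 10%.

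**Primary outcomes.** Protocol, Outcome variables, lists three. The first is "Pain history during the observation period, assessed as Yes/No at 12 months follow-up visit". The second is abscess history in the same form. The third is the number of teeth extracted or otherwise surgically treated, counted over the preceding year at the 12-month visit.

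**Baseline.** The same section introduces its list with "The patient’s primary examination will determine the following parameters". The list has four items: general and medical information, hygiene and diet, plaque, and lesion stage and activity. Work package 4 provides for documenting emergency treatment during follow-up.

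**The concern.** The conditions that bring the second stream to the clinic are the conditions that the primary outcomes count. A child may be in pain or have an abscess when randomised, or may have a tooth extracted soon afterwards because of the presenting problem. Nothing in the Protocol says whether that is an outcome event. Without baseline status, a later analysis cannot tell it from a new event or adjust for it, at least from the data that the Protocol lists.

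Events already under way at entry cannot reflect the effect of the study product. They are expected equally in every arm, so they raise all event rates and shrink the absolute difference. They can also be unevenly spread by chance. In addition, a planning rate taken from waiting-list children is not shown to apply to a sample that includes acute attenders.

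**Working it through.** **1. The plan's own figure.** Inputs from Sample size calculation: p_A = 0.30, p_B = 0.10, two-sided α = 0.05, τ = 9 comparisons, power 80%. The Fig 1 formula gives

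n = (0.30×0.70 + 0.10×0.90) × ((2.773 + 0.842)/0.20)² = 0.30 × (3.6145/0.20)² = 97.99, so 98.

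The stated 49 appears when 98 is divided by two. With 30% loss, 49/0.70 = 70, as stated. Whether 98 should have been halved is a separate question, and this point does not depend on it.

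**2. Can an entry episode be scored?** Set the definitions against three situations:

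- *Episode over before entry.* The pain and abscess wording limits the history to the observation period, so formally it does not count. But the start of that period is not defined, and the answer is a history taken up to a year later.
- *Episode still present at entry.* It falls inside the observation period on any natural reading, and no rule excludes it.
- *Extraction after randomisation for the presenting problem.* It falls inside the preceding year at the 12-month visit and adds to the count.

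The second and third situations can therefore be scored. None of the four listed baseline items identifies them.

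**3. Size.** The documents do not give the share of children affected. Let q be an assumed share of all children, equal in every arm, who are scored as events because of an entry episode. The observed rate is then p′ = p + q(1 − p), and the difference is 0.20 × (1 − q). This treats the outcome as one complication proportion, as the sample size section does.

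| q (assumed) | Placebo | Treatment | Difference | n per group from Fig 1, τ = 9 | Power, 98 per group, τ = 9 |
|---|---|---|---|---|---|
| 0 | 30.0% | 10.0% | 20.0 points | 98 | 80% |
| 3% | 32.1% | 12.7% | 19.4 points | 115 | 72% |
| 10% | 37.0% | 19.0% | 18.0 points | 157 | 54% |
| 30% | 51.0% | 37.0% | 14.0 points | 322 | 22% |

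Example at q = 10%: 0.30 + 0.10×0.70 = 0.37 and 0.10 + 0.10×0.90 = 0.19.

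The 3% row corresponds, for instance, to acute children forming 10% of the sample with 30% of them scored (0.10 × 0.30 = 0.03). The 30% row needs acute children to form 30% of the sample with every one of them scored.

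The table uses 98 per group so that the loss shown comes from this point alone. With 49 per group at τ = 9, power starts at 41% before any dilution and goes to 34%, 23% and 9%. The shortfall from 80% to 41% belongs to the halving, not to this point.

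**4. Does the stated intake fix q?** Ten acute children a day is 50 a week on an assumed five-day week, against 15 waiting-list consultations: 50/65 = 77% of presenters. These are children of eligible age who attend, not children enrolled. The figure shows that the acute stream need not be small, but it does not give q.

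**The case against.** Several things speak for the plan.

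- **The outcomes are restricted in time.** Limiting them to the observation period keeps out episodes that ended before entry. A reader might infer that every presenting episode is counted as a treatment failure. The documents do not support that. The exposure is confined to episodes still present at entry, extractions done for them afterwards, and misplaced recall.
- **Consent and baseline are at a separately assigned appointment** (Randomization, allocation and blinding), so some acute problems may be settled first. The Protocol neither requires nor records this.
- **The forms are not shown.** An acute-aid form and clinical examination forms are attached, and work package 2 says the baseline form includes risk-factor questions. With lesion charting and the emergency form, some extractions and treated abscesses may be traceable. It would go too far to say that baseline pain and abscess are certainly not collected. What stands is that they are not among the listed baseline parameters.
- **Randomisation balances the streams in expectation.** This is right. A reader might infer bias towards one product, but there is no basis for it. Dilution and chance imbalance remain.
- **The conflict about who is enrolled may be loose wording.** The information given to parents speaks of children in case they are waiting for GA, which suggests that some are not, and acute attenders may later join the list. The sections still need to agree.
- **The large power losses are a worst case.** This is accepted: the 30% row should not be read as a forecast.

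The point is also not a detail for an analysis plan, because baseline status that was never collected cannot be recovered in analysis.

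**Conclusion.** The point holds in a limited form. Participants and Ethics disagree on who is enrolled. If acute attenders are included, an episode present at entry or an extraction done for it can be scored as a primary event in any arm, and the listed data give no means to separate or adjust for it. The effect is dilution to 20 × (1 − q) points, with no expected direction between arms.

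The size rests on q, which the documents do not give. It is modest at q = 3% (about 32% vs 13%), material at q = 10% (37% vs 19%) and severe only in the worst case of q = 30% (51% vs 37%). These figures assume the same q in every arm, the planned 30% and 10% among the remaining children, and a single complication proportion. The sponsor should act because the remedy is cheap and has to be in place when children enter.

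**What to change.** 1. Reconcile Participants and Ethics on who is enrolled. If acute attenders stay, say why the 30% waiting-list rate is expected to apply to them, or revise it.
2. If both routes stay, record at baseline the entry route and yes/no items for current pain, abscess or fistula, and teeth already due for extraction, identified by tooth.
3. Define the observation period as starting at randomisation, and count extractions over that period in place of the preceding year.
4. Count pain and abscess at child level as new episodes with onset after randomisation. A tooth-level restriction would not suit them, because both are child-level yes/no histories. Leave out of the extraction count any tooth recorded at baseline as already due for extraction.
5. Adjust the primary analysis for entry route and baseline status. Stratifying randomisation by route is optional.

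The cost is the entry-route entry and two or three further form items, plus revised outcome wording. Entry-related events no longer count, so the primary outcomes describe new complications and not the child's whole burden over the year.

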Oral health is essential to general health and significantly influences the development of children. Dental caries has a high economic and social impact due both to the costs associated with its treatment as well as the societal cost of days lost in school by children, in the work by their parents and the sequels that remain throughout life (Wadhawan *et al.*, 2003). Also, since caries is associated with excessive sugar intake, it is a predictor of risk for cardiovascular disease and diabetes in children and adults. The aetiology of early childhood caries (ECC) is complex and the main associated factors are high sugar consumption and inadequate oral hygiene (Leong *et al.*, 2013). The traditional operative treatment of carious lesions often fails, especially when tooth restoration is performed at an early age (Raedel *et al.*, 2017). Less invasive caries treatment strategies have been proposed that would have the advantage of lowering the costs of care as well as decreasing the number of tooth extractions (Stephenson *et al.*, 2010). Fluoride applications are effective in decreasing the incidence of early childhood caries (Gao *et al.*, 2016) while SDF is effective in arresting the progression of cavitated lesions (Duangthip *et al.*, 2017). However, a usual adverse effect of SDF is that it stains the teeth black. New formulations have appeared that replace silver with copper (Tiefenfluorid), to avoid this. At this moment, the effectiveness of Tiefenfluorid to arrest carious lesions in permanent teeth is proven (Thneibat *et al.*, 2008), but there are no studies in deciduous dentition, or clinical studies comparing the effectiveness of all those non-invasive treatments. Also, there is a gap in knowledge about which protocols are most effective and how the interval between application influences clinical effectiveness (Slayton *et al.*, 2018). To date, it is known that a bi-annual application is better than one application per year, but other application protocols have not been studied (Crystal *et al.*, 2017). Due to the mechanisms of enamel and dentin remineralisation, this is a process where maximum fluoride concentration with maximum application frequency can provide the best results. A new six-arm clinical trial could provide important information on the efficacy, cost-effectiveness and potential side-effects of these methods for patients.

Study design and settings

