D6.2 Conference abstracts.

D6.3 Publication about the effectiveness of SDF and Tiefenfluorid treatment in preschool children with S-ECC (to be published in Caries Research (impact factor: 2.188) or in BMC Oral Health (impact factor: 1.602).

D6.4 Publication about the effectiveness of fluoride treatment according to the type of carious lesion in deciduous dentition (to be published in the International Journal of Paediatric Dentistry (impact factor: 2.18) or in European archives of paediatric dentistry: official journal of the European Academy of Paediatric Dentistry (impact factor: 1.48).

D6.5 Evidence-based recommendations and economic evaluation report for national policymakers.

Milestones of WP6

MS6.1 Meeting with Communication Department and IT department of RSU.

MS6.2 Scientific conferences.

MS6.3 Meeting with policymakers.

Gantt chart

The workflow in each work packages and relevant deliveries are illustrated in the Gantt chart (Fig 4.).

[figure not shown]

Fig 4. The Gantt chart of the clinical trial.

Risks

1. Research achievability risks
 - a. Number of patients recruited less than expected - sample size calculation was estimated using conservative assumptions. The expected difference in the prevalence of severe caries complications in different treatment groups and the placebo group is expected to be 20% (10% complication rate for treatment groups and 30% for placebo). From previous studies, the expected prevalence in treatment groups could be even less, meaning the observed difference would be greater. In such a case, statistical power can be achieved even with a lower number of patients.
 - b. Loss of follow-up – we plan to include 70 patients in every group in order to ensure that there are still at least 49 in every group at the end of the project (we assume the potential loss of follow-up examinations to be 30%, which we consider to be sufficient).
2. Research methodology risks

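### The 10% complication rate assumed for SDF and Tiefenfluorid is a conventional-treatment figure presented as a ceiling, and neither the stated 80% power nor the reassurance about under-recruitment holds on the protocol's own formula.

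*Protocol*

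**What the plan says.** The section *Sample size calculation* bases the active-arm rate on one source: "From previous studies it is known that conventionally treating early childhood tooth caries, the frequency of complications is 10" per cent. For the comparison rate it uses the clinic's own records of children waiting for general anaesthesia "who receive no additional treatment, is approximately 30" per cent. It then concludes: "therefore in the study's treatment groups we expect that the frequency of complications will be no greater than 10" per cent, "but in the placebo groups - 30" per cent. From these two rates it obtains 49 children per group "with α error 0.05 and with a study capacity of 80" per cent, raised to 70 per group for losses, with 9 comparisons entered in the Fig 1 formulas.

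Under *Interventions*, the six groups receive placebo varnish, SDF or Tiefenfluorid, each on two schedules, and "caries tissue removal will not be performed; the products will be applied to dried teeth". Under *Ethics*, conventional treatment is what children who decline the study receive.

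The opening background says of Tiefenfluorid that it is proven in permanent teeth, "but there are no studies in deciduous dentition, or clinical studies comparing the effectiveness of all those non-invasive treatments".

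*Risks*, item 1a, describes the sample size assumptions as conservative and adds: "From previous studies, the expected prevalence in treatment groups could be even less, meaning the observed difference would be greater". It goes on to say that power could then be reached with fewer patients. It gives no figure and no citation.

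**The concern.** A complication rate seen under one treatment does not set an upper limit for a different one. The protocol joins the two with *therefore* and *no greater than*, so a borrowed figure reads as a derived bound. The 20-point difference rests on it, and so does the stated power.

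Item 1a of *Risks* then considers error in one direction only. It treats an active rate below 10% as a reason not to worry about a recruitment shortfall and does not consider a rate above 10%. A sponsor relying on that text could accept fewer children in the belief that power is protected. By the protocol's own formula, power at the planned group size is already well below 80% when 10% is taken at face value.

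**Working it through.** **Inputs.** From *Sample size calculation*: placebo rate 30%, active rate 10%, alpha 0.05, power 80%, τ = 9 comparisons, 49 evaluable per group, 70 enrolled per group. From *Risks* 1b: 30% loss. The placebo rate is held at 30% throughout. Active rates other than 10% are assumptions, because the protocol gives none for SDF or Tiefenfluorid.

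**Step 1: the protocol's own figure.** Fig 1 gives

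n = [p_A(1 − p_A) + p_B(1 − p_B)] × [(z₁₋α/(2τ) + z₁₋β)/(p_A − p_B)]²

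Here z at 1 − 0.05/18 is 2.773 and z at 0.80 is 0.842.

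- Variance term: 0.30 × 0.70 + 0.10 × 0.90 = 0.30.
- n = 0.30 × (3.615/0.20)² = 97.99, so 98.

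This n is a per-group number: the power formula in the same figure divides each variance by n. The Fig 1 legend describes n as covering two equivalent groups, and 97.99/2 = 48.99, which is the protocol's 49. The later steps reproduce: 49/(1 − 0.30) = 70, 6 × 49 = 294 and 6 × 70 = 420.

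**Step 2: power at 10%.** Fig 1 gives power = Φ(z − 2.773) + Φ(−z − 2.773), with z = 0.20/√(0.30/n). The second term is negligible.

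- n = 49: z = 2.556, Φ(−0.217) = 0.414.
- n = 98: z = 3.615, Φ(0.842) = 0.800.

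The stated 80% belongs to 98 per group. At 49 it is 41%.

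**Step 3: dependence on the 10%.** The same formulas with other active rates:

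| Active rate | n per group for 80% power | Power at 49 per group | Power at 98 per group |
|---|---|---|---|
| 5% (assumed) | 54 | 75% | 98% |
| 10% (protocol) | 98 | 41% | 80% |
| 12.5% (assumed) | 137 | 27% | 62% |
| 15% (assumed) | 196 | 17% | 41% |
| 20% (assumed) | 484 | 5% | 13% |

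The last column separates the two problems. At 98 per group the arithmetic error is gone, and what remains is sensitivity to the 10% alone: an active rate of 15% would cut power from 80% to 41%.

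**Step 4: what the reassurance in *Risks* 1a would need.** Solving the power formula for the active rate that gives 80%:

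- 49 evaluable per group: about 4.2%.
- 70 evaluable per group (no losses at all): about 7.3%.

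Fewer patients than these would need a still lower rate. The protocol offers no figure in support of any of these rates.

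**The case against.** The protocol does not hide the source. It says the 10% comes from conventional treatment and words the active rate as an expectation. Every superiority trial assumes an effect before it is known, and matching a benchmark treatment is a defensible target. The background also gives some rationale: operative treatment often fails at an early age, less invasive strategies would mean fewer extractions, and SDF arrests cavitated lesions. The sentence in *Risks* 1a is conditional, and it is true that a larger difference needs fewer patients.

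Much of this stands, and it limits what can be said. Several stronger readings are tempting but not supported:

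- *That the true effect is not 20 points.* Nothing in the protocol contradicts 10%. The figure lacks support from data on the products tested.
- *That the two rates come from different populations.* The protocol describes its own children but not those behind the 10% figure, so this cannot be judged.
- *That the protocol denies any evidence in primary teeth.* The statement about deciduous dentition concerns Tiefenfluorid. For SDF a study is cited, on lesion arrest. The appeal to previous studies in *Risks* 1a is thus unreferenced for SDF, and unsupported by the protocol's own account for Tiefenfluorid.
- *That the trial could not show a realistic effect.* The protocol gives no basis for calling any particular active rate realistic.
- *That the low power at 49 comes from the source of the 10%.* At an active rate of 10%, the fall from 80% to 41% is due entirely to halving the formula's n.

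What the objection does not rescue is the wording as an upper limit, the label conservative, or the stated 80%.

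**Conclusion.** The point holds in a limited form. The 10% active rate comes from a treatment that no arm receives, and the protocol gives no complication rate for SDF or Tiefenfluorid. It is a design assumption and should not be presented as a derived ceiling or as conservative.

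On the Fig 1 formula with two-sided alpha 0.05, 9 comparisons and placebo at 30%, the planned 49 evaluable per group give 41% power at the protocol's own 10%. Over assumed active rates of 5% to 20%, power runs from 75% to 5%, so 80% is not reached anywhere in that range. The reassurance about under-recruitment would need an active rate below about 4.2% at 49 evaluable per group, or below about 7.3% if all 70 were evaluable.

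The section and the risk item should be corrected. This does not show that either product will do worse than 10%.

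**What to change.** In *Sample size calculation*:

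- State that 10% is a design assumption taken from conventional treatment, and remove *therefore* and *no greater than*.
- Replace the stated 80% with the power at 49 evaluable per group for active rates of 5%, 10%, 12.5%, 15% and 20% (75%, 41%, 27%, 17% and 5%), with the assumed rates marked as such.

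In *Risks* 1a:

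- Delete the word conservative and the sentences saying that the active rate could be lower and that power could be kept with fewer patients.
- State instead that a recruitment shortfall lowers power further.

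The cost is wording in two places and a five-row table. No extra patients are needed for this change. The downside is that the stated power becomes less favourable.
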